9.2.3. Safety Procedures

9.2.3.1. Body Weight and Height

Body weight and height will be determined at time points according to time points in [Table 1](#).

9.2.3.2. Physical Examination

A complete physical examination will be performed at time points according to [Table 1](#). Care should be taken to examine and assess any abnormalities that may be present, as indicated by the participant's medical history.

9.2.3.3. Laboratory Testing

Pregnancy testing samples using urine sticks will be analyzed by each study site. Detailed instructions for urine sample collection are in the package insert available at study sites.

9.2.4. Drug Concentration and Measurements

Serum samples for measuring functional dupilumab concentrations will be collected at time points according to [Table 1](#). In the event of suspected SAEs, such as anaphylaxis or hypersensitivity, additional blood samples may be collected at or near the event for PK assessment. Detailed instructions for blood sample collection are included in the laboratory manual provided to study sites.

Any unused or residual samples may be used for exploratory biomarker research.

9.2.5. Pharmacodynamic and Exploratory Biomarker Procedures

In this study, research assessments will be performed to explore AD, how dupilumab may modify the underlying the disease process in AD, type 2 inflammation, and predictors of dupilumab safety and efficacy.

Samples for total IgE and allergen-specific IgEs will be collected at time points according to in [Table 1](#). The biomarkers studied are believed to be relevant to the pathophysiology of AD in participants with skin of color, response to treatment (ie, assessment of type 2 inflammation) and baseline predictors of response and dupilumab mechanism of action.

IL-4 and IL-13 regulate B cell class switching to, as well as production of, IgE. Dupilumab has been shown to suppress IgE (total and allergen-specific) in AD, asthma, and nasal polyposis patients. Serum concentrations of IgE (total and a panel of allergen-specific) will be measured at time points indicated in [Table 1](#). Modulation of IgE is a known pharmacodynamic marker for dupilumab in AD. Data analysis will be described in the SAP and the results will be provided in the CSR.

9.2.5.1. Residual Samples

Residual samples for study-related research (eg, blood, serum, plasma) will be stored for up to 15 years after the final date of the database lock (or for a shorter time period if required per regional laws and regulations). The samples may be utilized for exploratory research that may or may not be related to dupilumab safety and/or efficacy, the progression and clinical outcomes of AD and related diseases, the biology of IL-4R, IL-4, IL-13, and related pathways and/or for assay development and/or validation. The results of these exploratory research analyses will not be presented in the CSR.

9.2.5.2. Serum and Plasma for Exploratory Research

Serum and plasma for exploratory research will be collected and banked for exploratory research related to dupilumab safety and/or efficacy, the progression, disease activity and clinical outcomes of AD and related diseases, and the biology of IL-4Ra and related pathways.

9.2.6. Future Biomedical Research (Optional)

Participants/parents or legal guardians who agree to participate in the future biomedical research (FBR) substudy will be required to consent to this optional substudy before samples are banked for FBR. Additional samples will be collected for FBR according to Schedule of Events [Table 1](#). Residual biomarker samples for study-related research will be stored for up to 15 years after the final date of the database lock (or for a shorter time period if required per regional laws and regulations). The samples may be utilized for FBR that may or may not be directly related to the study, including being used as reference samples and assay development or validation. The results of these FBR analyses will not be presented in the CSR.

9.2.7. Pharmacogenomic Analysis (Optional)

Participants/parent or legal guardians who agree to participate in the genomics substudy will be required to consent to this optional substudy before collection of the samples. Whole blood samples for DNA extraction should be collected on day 1/baseline (predose), but can be collected at a later study visit. DNA samples will be collected for pharmacogenomics analyses to understand the genetic determinants of efficacy and safety associated with the treatments in this study and the molecular basis of AD and related diseases. These samples will be single-coded as defined by the International Council on Harmonisation (ICH) guideline E15. Samples will be stored for up to 15 years after the final date of the database lock (or for a shorter time period if required per regional laws and regulations). If there are specific site or country requirements involving the pharmacogenomic analyses which the sponsor is unable to comply with, samples will not be collected at those sites.

The purpose of the pharmacogenomic analyses is to identify genomic associations with clinical or biomarker response to dupilumab, other AD clinical outcome measures and possible AEs. In addition, associations between genomic variants and prognosis or progression of AD as well as related allergic/atopic diseases may also be studied. These data may be used or combined with data collected from other studies to identify and validate genomic markers related to the study drug, target pathway, or AD and related diseases.

Analyses may include sequence determination or single nucleotide polymorphism studies of candidate genes and surrounding genomic regions. Other methods, including whole-exome sequencing, whole-genome sequencing, and DNA copy number variation may also be performed. The list of methods may be expanded to include novel methodology that may be developed during the course of this study or sample storage period. Results from the genomic analyses will not be reported in the CSR.

Research findings from the optional genomic substudy will not be disclosed to the participant or principal investigator, even if they have implications for a participant's health and management. Genetic results from this substudy are for research purposes only and not for medical diagnosis or for reproductive decision-making.

10. SAFETY EVALUATION AND REPORTING

10.1. Recording and Reporting Adverse Events

10.1.1. General Guidelines

The investigator must promptly record all clinical events occurring during the study data collection, from the time of signing the ICF to the end of on-treatment period (see Section 11.4.5.1). Medical conditions that existed or were diagnosed prior to the signing of the Informed Consent will be recorded as part of medical history. Abnormal laboratory values and vital signs observed at the time of Informed Consent should also be recorded as medical history. Any subsequent worsening (ie, any clinically significant change in frequency and/or intensity) of a pre-existing condition that is temporally associated with the use of the study drug should also be recorded as an AE.

At each visit, the investigator will determine whether any AEs have occurred by evaluating the participant. Adverse events may be directly observed, reported spontaneously by the participant, or by questioning the participant at each study visit. Participant should be questioned in a general way, without asking about the occurrence of any specific symptoms. The Investigator must assess all AEs to determine seriousness, severity, and causality, in accordance with the definitions in Section 10.2. The Investigator's assessment must be clearly documented in the site's source documentation with the Investigator's signature. The Investigator should follow up on SAEs (and AESIs) until they have resolved or are considered clinically stable; AEs should be followed until they are resolved or last study visit, whichever comes first.

Always report the diagnosis as the AE or SAE term. When a diagnosis is unavailable, report the primary sign or symptom as the AE or SAE term with additional details included in the narrative until the diagnosis becomes available. If the signs and symptoms are distinct and do not suggest a common diagnosis, report them as individual entries of AE or SAE.

Laboratory results, vital signs, and other diagnostic results or findings should be appraised by the Investigator to determine their clinical significance. Isolated abnormal laboratory results, vital sign findings, or other diagnostic findings (ie, not part of a reported diagnosis) should be reported as AEs if they are symptomatic, lead to study drug discontinuation, dose reduction, require corrective treatment, or constitute an AE in the investigator's clinical judgment.

For events that are serious due to hospitalization, the reason for hospitalization must be reported as the SAE (diagnosis or symptom requiring hospitalization). A procedure is not an AE or SAE, but the reason for the procedure may be an AE or SAE. Pre-planned (prior to signing the ICF) procedures, treatments requiring hospitalization for pre-existing conditions that do not worsen in severity, and admission for palliative or social care should not be reported as SAEs (see Section 10.2 for Definitions).

For deaths, the underlying or immediate cause of death should always be reported as an SAE.

Any SAE that may occur subsequent to the reporting period (end of the on-treatment period) that the Investigator assesses as related to study drug should also be reported.

All AEs, SAEs, AESIs, and pregnancy reports are to be reported according to the procedures in Section 10.1.3.

10.1.2. Reporting Procedure

All events (serious and non-serious) must be reported with investigator's assessment of the event's seriousness, severity, and causality to the (when applicable: blinded) study drug. For SAEs and AESIs, a detailed narrative summarizing the course of the event, including its evaluation, treatment, and outcome should be provided on the AE CRF. Specific or estimated dates of event onset, treatment, and resolution should be included, when available. Medical history, concomitant medications, and laboratory data that are relevant to the event should also be summarized in the narrative. For fatal events, the narrative should state whether an autopsy was or will be performed, and include the results if available. Information not available at the time of the initial report must be documented in a follow-up report. Source documents (including hospital or medical records, diagnostic reports, etc) will be summarized in the narrative on the AE CRF, and retained at the study center and available upon request.

Urgent safety queries must be followed up and addressed promptly. Follow-up information and response to non-urgent safety queries should be combined for reporting to provide the most complete data possible within each follow-up.

10.1.3. Events that Require Expedited Reporting to Sponsor

The following events also require reporting to the sponsor (or designee) within 24 hours of learning of the event:

- **SAEs**
- **Adverse Events of Special Interest (AESIs; serious and nonserious):** Adverse events of special interest for this study include the following:
 - Anaphylactic reactions
 - Systemic hypersensitivity reactions
 - Helminthic infections
 - Any severe type of conjunctivitis or blepharitis
 - Keratitis
 - Clinically symptomatic eosinophilia (or eosinophilia associated with clinical symptoms)
- Any participant who experiences an AESI related to an eye disorder will be referred to an ophthalmologist if deemed necessary by the investigator. Further evaluation of these AESIs will be performed including any additional tests, as per the discretion of the ophthalmologist.
- **Pregnancy:** Although pregnancy is not considered an AE, it is the responsibility of the investigator to report to the sponsor (or designee), within 24 hours of identification, any pregnancy occurring in a female, during the study or within 12 weeks of the last dose of study drug. Any complication of pregnancy affecting a female study participant and/or fetus and/or newborn that meets the SAE criteria must be reported as an SAE. Outcome for all pregnancies should be reported to the sponsor.

10.2. Definitions

10.2.1. Adverse Event

An AE is any untoward medical occurrence in a participant administered a study drug which may or may not have a causal relationship with the study drug. Therefore, an AE is any unfavorable and unintended sign (including abnormal laboratory finding), symptom, or disease which is temporally associated with the use of a study drug, whether or not considered related to the study drug (ICH, 1994).

For studies with PROs, the PRO data are generally not reportable as individual AEs and thus will not be reported or reconciled as such.

10.2.2. Serious Adverse Event

An SAE is any untoward medical occurrence that at any dose:

- Results in **death** – includes all deaths, even those that appear to be completely unrelated to study drug (eg, a car accident in which a participant is a passenger).
- Is **life-threatening** – in the view of the investigator, the participant is at immediate risk of death at the time of the event. This does not include an AE that had it occurred in a more severe form, might have caused death.
- Requires in-patient **hospitalization or prolongation of existing hospitalization**. In-patient hospitalization is defined as a hospital admission (any duration) or an emergency room visit for longer than 24 hours. Prolongation of existing hospitalization is defined as a hospital stay that is longer than was originally anticipated for the event, or is prolonged due to the development of a new AE as determined by the investigator or treating physician.
- Results in persistent or significant **disability/incapacity** (substantial disruption of one's ability to conduct normal life functions).
- Is a **congenital anomaly/birth defect**
- Is an **important medical event** - Important medical events may not be immediately life-threatening or result in death or hospitalization, but may jeopardize the participant or may require intervention to prevent one of the other serious outcomes listed above (eg, intensive treatment in an emergency room or at home for allergic bronchospasm; blood dyscrasias or convulsions that do not result in hospitalization; or development of drug dependency or drug abuse).

Criteria for reporting SAEs must be followed for these events.

10.2.3. Adverse Events of Special Interest

An AESI (serious or non-serious) is one of scientific and medical interest specific to the sponsor's product or program, for which ongoing monitoring and rapid communication by the investigator to the sponsor can be appropriate. Such an event might warrant further investigation in order to characterize and understand it.

10.2.4. Severity

The severity of AEs will be graded according to the following scale:

Mild: Does not interfere in a significant manner with the participant normal functioning level. It may be an annoyance. Prescription drugs are not ordinarily needed for relief of symptoms, but may be given because of personality of the participant.

Moderate: Produces some impairment of functioning but is not hazardous to health. It is uncomfortable or an embarrassment. Treatment for symptom may be needed.

Severe: Produces significant impairment of functioning or incapacitation and is a definite hazard to the subject's health. Treatment for symptom may be given and/or participant hospitalized.

If a laboratory value is considered an AE, its severity should be based on the degree of physiological impairment the value indicates.

Injection Site Reactions

The severity of ISRs will be graded according to the following scale (semi-colon indicates "or" within description of grade):

Mild: Pain that does not interfere with activity; mild discomfort to touch; <5 cm of erythema or induration that does not interfere with activity

Moderate: Pain that requires repeated use of non-narcotic pain reliever >24 hours or interferes with activity; discomfort with movement; 5.1 cm to 10 cm erythema or induration or induration that interferes with activity

Severe: Pain that requires any use of narcotic pain reliever or that prevents daily activity; significant discomfort at rest; >10 cm erythema or induration; prevents daily activity; requires emergency room (ER) visit or hospitalization; necrosis or exfoliative dermatitis

10.2.5. Causality

The investigator must provide causality assessment as whether or not there is a reasonable possibility that the drug caused the adverse event, based on evidence or facts, his/her clinical judgment, and the following definitions. The causality assessment must be made based on the available information and can be updated as new information becomes available.

Include the following when applicable] For double blinded studies using an active comparator, the investigator should consider all study drugs in determining event causality.

The following factors should be considered when assessing causality:

- Temporal relationship: time to onset vs time drug was administered
- Nature of the reactions: immediate vs long term
- Clinical and pathological features of the events
- Existing information about the drug & same class of drugs
- Concomitant medications
- Underlying and concurrent illnesses

- Response to dechallenge (drug discontinuation) or dose reduction
- Response to rechallenge (re-introduction of the drug) or dose increase, when applicable
- Participant's medical and social history

Causality to the study drug (including study drug administration):

- Related:
 - The AE follows a reasonable temporal sequence from study drug administration, and cannot be reasonably explained by the nature of the reaction, participant's clinical (eg, disease under study, concurrent diseases, concomitant medications), or other external factors.
- or
- The AE follows a reasonable temporal sequence from study drug administration, and is a known reaction to the drug under study or its class of drugs, or is predicted by known pharmacology.
- Not Related:
 - The AE does not follow a reasonable sequence from study drug administration, or can be reasonably explained by the nature of the reaction, participant's clinical state (eg, disease under study, concurrent diseases, and concomitant medications) or other external factors.

Causality to the study conduct (protocol specified procedure):

- Related:
 - The AE follows a reasonable temporal sequence from a protocol specified procedure, and cannot be reasonably explained by the nature of the reaction, participant's clinical (eg, disease under study, concurrent diseases, concomitant medications), or other external factors.
- Not Related:
 - The AE does not follow a reasonable sequence from a protocol specified procedure, or can be reasonably explained by the nature of the reaction, participant's clinical state (eg, disease under study, concurrent diseases, and concomitant medications) or other external factors.

10.3. Safety Monitoring

The investigator will monitor the safety of study participant at his/her site(s) as per the requirements of this protocol and consistent with current Good Clinical Practice (GCP). Any questions or concerns should be discussed with the sponsor in a timely fashion. The sponsor will monitor the safety data from across all study sites. The Medical/Study Director will have primary responsibility for the emerging safety profile of the compound, but will be supported by other departments (eg, Global Patient Safety [GPS]; Biostatistics and Data Management). Safety monitoring will be performed on an ongoing basis (eg, individual review of SAEs) and on a periodic cumulative aggregate basis.

10.4. Notifying Health Authorities, Institutional Review Board /Ethics Committee, and Investigators

During the study, the sponsor and/or the CRO will inform health authorities, IECs/IRBs, and the participating investigators of any SUSARs (Suspected Unexpected Serious Adverse Reactions) occurring in other study centers or other studies of the active study drug (dupilumab), as appropriate per local reporting requirements. In addition, the sponsor and/or CRO will comply with any additional local safety reporting requirements.

Upon receipt of the sponsor's notification of a SUSAR that occurred with the study drug, the investigator will inform the IEC/IRB unless delegated to the sponsor.

Event expectedness for study drug (dupilumab) is assessed against the Reference Safety Information section of the Investigator's Brochure that is effective for expedited safety reporting.

At the completion of the study, the sponsor will report all safety observations made during the conduct of the trial in the CSR to health authorities and IECs/IRB as appropriate.

11. STATISTICAL PLAN

11.1. Statistical Hypothesis

There is no formal statistical hypothesis testing and no planned inferential comparisons in this study.

11.2. Justification of Sample Size

The enrolled population will attempt to approximate the US census bureau data on proportions of self-reported races that comprise the skin of color population in the United States— to this end all self-reported races representing skin of color will be included, however a cap at approximately 40% will be set for non-black/non-African American participants.

Due to the descriptive character of this study, no formal sample size calculation will be performed. The sample size of this study is chosen empirically to support descriptive analysis of efficacy and safety in the overall skin of color population. With up to a potential 15% drop out rate based on prior studies, 120 participants would yield approximately 105 participants overall.

11.3. Analysis Sets

11.3.1. Full Analysis Set

The full analysis set (FAS) includes all participants who are enrolled in the study and have at least 1 post-baseline efficacy assessment. The FAS is the main analysis population for the study and will be used to summarize baseline characteristics and disposition and to analyze efficacy variables.

11.3.2. Safety Analysis Set

The safety analysis set (SAF) includes all participants in the FAS who are enrolled and received at least 1 dose of dupilumab during the study. Treatment compliance and administration, and all safety variables will be analyzed using the SAF.

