Patient- Reported Outcome Measures: Peak Pruritus NRS, Sleep Quality NRS, Skin Pain NRS, Dyspigmentation NRS, Xerosis NRS, Children’s Dermatology Life Quality Index, Dermatology Life Quality Index, Hospital Anxiety and Depression Scale, POEM, PGID, PGIC

Investigator- Reported Outcome Measures: EASI, IGA, SCORing Atopic Dermatitis, Body Surface Area Involvement of Atopic Dermatitis, AD phenotypic description (primary morphologies, and distribution), Post-inflammatory hyperpigmentation severity scale

Substudies: Photography (select sites), Colorimetry measurement (select sites), Optical Coherence Tomography (OCT) and additional optional non-invasive *in vivo* imaging (single site) at AD lesional, hyperpigmentation lesional, and non-lesional targets

Safety procedures and assessments: adverse event (AE), physical examination, and clinical laboratory testing

Pharmacokinetics (PK): Serum samples will be collected at specified time points for assay of dupilumab concentration.

Statistical Plan**Justification of Sample Size**

Due to the descriptive character of this study, no formal sample size calculation will be performed. The sample size of this study is chosen empirically to support descriptive analysis of efficacy and safety in the overall skin of color population. With up to a potential 15% drop out rate based on prior studies, 120 participants would yield 105 participants overall.

Analysis Sets:***Full Analysis Set (FAS)***

The full analysis set (FAS) includes all participants who are enrolled in the study and have at least 1 post-baseline efficacy assessment. The FAS is the main analysis population for the study and will be used to summarize baseline characteristics and disposition and to analyze efficacy variables.

Safety Analysis Set (SAF)

The safety analysis set (SAF) includes all participants in the FAS who are enrolled and received at least one dose of dupilumab during the study. Treatment compliance and administration, and all safety variables will be analyzed using the SAF.

Pharmacokinetic Analysis Sets

The PK analysis population includes all participants who received any study drug and who had at least 1 non-missing result following the first dose of study drug.

Statistical Methods:

All statistical analyses will be descriptive.

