11.4.5. Safety Analysis

Safety analysis will be based on the SAF. This includes reported TEAEs and other safety data (ie, physical exam).

A descriptive summary of safety results will be presented for each study part.

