3.1. Full Analysis Set (FAS)

The full analysis set (FAS) includes all participants who are enrolled in the study and have baseline assessment. The FAS is the main analysis population for the study and will be used to summarize patient disposition, baseline characteristics and to analyze efficacy variables.

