3.2. The Safety Analysis Set (SAF)

The safety analysis set (SAF) includes all participants in the FAS who are enrolled and received at least 1 dose of dupilumab during the study. Treatment administration, compliance and all safety variables will be analyzed using the SAF.

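### The protocol limits the safety set to participants with an efficacy score after baseline, the SAP in practice keeps everyone dosed, and both use the same names; the effect is probably very small

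*Protocol*

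**What the plan says.** **Protocol.** Section 11.3.1 says that the FAS "includes all participants who are enrolled in the study and have at least 1 post-baseline efficacy assessment" and that it "will be used to summarize baseline characteristics and disposition and to analyze efficacy variables". Section 11.3.2 then takes the safety set from inside the FAS: "The safety analysis set (SAF) includes all participants in the FAS who are enrolled and received at least 1 dose of dupilumab". It adds: "Treatment compliance and administration, and all safety variables will be analyzed using the SAF". Section 11.4.5 repeats the choice of population: "Safety analysis will be based on the SAF". The synopsis carries the same nesting: "The safety analysis set (SAF) includes all participants in the FAS who are enrolled and received at least one dose of dupilumab".

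**SAP.** Section 3.1 gives a different entry condition. There the FAS "includes all participants who are enrolled in the study and have baseline assessment". Section 3.2 keeps the nesting, so the SAF "includes all participants in the FAS who are enrolled and received at least 1 dose of dupilumab during the study". Section 5.1 runs disposition on the FAS, although its list begins with the screened and enrolled counts. The SAP does not say that its FAS differs from the protocol's or why.

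**The concern.** Whether a dosed participant has an efficacy score has no bearing on whether that participant's adverse events should count. If it decides membership of the safety set, the exclusion is informative, because those at risk of being left out are people who stop almost at once after the first dose. Protocol 8.4.2.1 makes a serious or severe related allergic reaction a reason to stop drug permanently, and 10.1.3 lists anaphylactic and systemic hypersensitivity reactions as AESIs. These are events that could occur before any efficacy score.

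Safety is a secondary objective and the study has at most 120 participants, so one early event can decide whether a rare AESI appears in the tables at all. The protocol also assigns disposition to the FAS, so the same person would be missing from the discontinuation reasons. The PK set in Protocol 11.3.3 is not nested in the FAS. A participant who reacts, gives the event-driven PK sample allowed in 9.2.4 and then leaves could be in the PK set but not in the safety set.

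With two definitions under one name, the safety denominator also depends on which document is followed, and neither document says which prevails.

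**Working it through.** **Step 1. The sets side by side.** Let E = enrolled, D = dosed, B = has a baseline assessment, P = has an efficacy assessment after baseline.

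| | FAS | SAF |
|---|---|---|
| Protocol 11.3.1, 11.3.2, synopsis | E and P | E and P and D |
| SAP 3.1, 3.2 | E and B | E and B and D |

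The sets differ for any participant who is dosed and has B but not P. Call the number of such participants k.

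**Step 2. Who satisfies B.** Inclusion criteria 4 to 6 (Protocol 7.2.1) require EASI, IGA and BSA at screening and at baseline. Protocol 9.2 places assessments before dosing. SAP 6.1 takes the latest valid pre-dose value as baseline. A properly enrolled and dosed participant therefore has B, and the SAP's SAF equals all dosed participants.

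**Step 3. Who fails P.** Three routes give a score after dosing:
- Week 2 clinic visit. The schedule puts it at day 15 ± 3, so day 12 at the earliest. Week 1 is a phone visit with no clinic score.
- Diary itch score. Peak Pruritus NRS is an efficacy variable (Protocol 5.2) and is recorded daily (9.2.2.1.1). SAP 6.3 ends the diary baseline at day 1, so one entry on day 2 is enough.
- Early termination visit. It includes the end-of-study assessments (Protocol 9.1.2 and schedule footnote 3).

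Only a participant who misses all three counts towards k.

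**Step 4. Size of the sets.** The documents give no value for k. The only related figure is the dropout allowance of up to 15%: 120 × 0.85 = 102, which the protocol states as approximately 105. That allowance covers all dropout over 24 weeks, so 120 × 0.15 = 18 is a ceiling for k and not an estimate. Assuming that all 120 are dosed with a baseline assessment:

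- Protocol SAF = 120 − k: 119 for k = 1, 118 for k = 2, 102 at the ceiling of k = 18.
- SAP SAF = 120 for every k.

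**Step 5. Effect on an event rate (assumed).** Suppose that each of the k participants has an AESI and no one else does. Limits are two-sided exact 95% (Clopper-Pearson). With 0 events in n, the upper limit is 1 − 0.025^(1/n).

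| k | All dosed, as in the SAP | Protocol SAF |
|---|---|---|
| 1 | 1/120 = 0.83% (0.02% to 4.56%) | 0/119; upper limit 1 − 0.025^(1/119) = 3.05% |
| 2 | 2/120 = 1.67% (0.20% to 5.89%) | 0/118; upper limit 1 − 0.025^(1/118) = 3.08% |

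FAS-based discontinuations would likewise be short by k under the protocol. The intervals only show scale; the plan is descriptive.

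**The case against.** The strongest reply is that the SAP, the document that specifies the analysis in detail, already keeps the early leaver. By step 2 its nested SAF is the set of all dosed participants, so following the SAP no event is lost. This stands, and it limits the point to an unreconciled conflict plus a cross-reference to the FAS that serves no purpose.

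The second reply is that k is likely to be close to zero even under the protocol. One diary entry or an attended early termination visit qualifies a participant, and those who stop drug are encouraged to stay in the study (Protocol 8.4.2). This also stands, as a limit on size. It does not make an efficacy score a sound condition for entering a safety set.

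Third, the safety signal itself is not lost. SAEs and AESIs go to the sponsor within 24 hours (Protocol 10.1.3), and 10.4 commits the sponsor to reporting all safety observations in the study report. This stands: only the SAF-based tables are exposed.

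A reader might go further and infer any of the following, which the documents do not support:
- **That the early leaver vanishes from all disposition output.** Protocol 11.4.1 and SAP 5.1 both count screened and enrolled participants, and screen failures cannot belong to the FAS. What is at risk is the FAS-based discontinuation count and its reasons.
- **That the SAP newly admits undosed participants to the FAS.** The protocol FAS has no dosing condition either, so adding one is a preference.
- **That the primary result is affected.** SAP 5.7.1 uses participants with a week 24 EASI as the denominator, so the difference in FAS does not move the primary estimate.
- **That the SAP's empty revision history hides the change.** SAP 1.2.4 concerns amendments to the SAP itself.

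**Conclusion.** The point holds as a real but small error. As written, the protocol and its synopsis exclude a dosed participant with no efficacy assessment after baseline from SAF-based safety summaries and from FAS-based discontinuation counts and reasons. The SAP in practice does not. The same two names therefore denote different populations, with no explanation.

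The documents do not support the stronger conclusion that the trial's safety tables will omit early reactors. That follows only if the protocol definition is the one applied, and only for someone with no diary entry, clinic score or early termination visit after dosing.

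The size rests on an assumed k. With k = 1 and one AESI, 0.8% becomes 0% of 119; with k = 0 nothing changes. This is a consistency correction worth making before the analysis sets are fixed, and it does not threaten the study's conclusions.

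**What to change.** 1. In Protocol 11.3.2, the synopsis and SAP 3.2, define the SAF as all participants given one or more doses of dupilumab, and delete the reference to the FAS.
2. Use one FAS definition in the protocol, its synopsis and the SAP, with no post-baseline condition. The SAP 3.1 condition is sufficient.
3. In Protocol 11.3.1 and SAP 5.1, base disposition on all enrolled participants, and base the screening counts on all screened participants.

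The cost is minor rewording of these sections, with no new data and no change to conduct. Event rates may come out slightly less favourable than under the protocol definition. They would match what the SAP already gives if every dosed participant has a baseline assessment.
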